1.3 Research Design and Methods

We will conduct a randomized clinical trial enrolling eligible participants who are determined to be SARS-CoV-2-positive (e.g., via Rutgers Corona Cohort [RCC] study, hospital or other screening programs) who volunteer for the study. Specifically, we will enroll 70 participants whose test has been performed within the past 7 days who are either asymptomatic or mildly symptomatic at baseline. Mild COVID-19 symptoms include new cough, sore throat, fever, myalgias, new vomiting or diarrheaor change in smell or taste. Illness requiring hospitalization, or those who present with hypoxia (PO2<92%) or shortness of breath at time of enrollment will be classified as significantly symptomatic and excluded from study participation. People who are allergic or intolerant to NTZ, RBV or HCQ will be excluded. We will randomly allocate participants stratified by presence of mild symptoms to 1) NTZ, RBV and HCQ or 2) placebo. Treatment with the investigational agents or placebo will continue for 5 days. Viral load will be assessed at baseline (day 0) as well as at days 3, 6, and 10 to monitor response to antiviral treatment. Immune status will be determined by antibody testing of blood collected at baseline and day 28.

Prior to initiating enrollment, we will prepare two randomization tables for treatment assignment using permuted blocks of six which will be provided to the research pharmacist. One table will be used for participants without symptoms and the other will be used for those with mild symptoms. The pharmacist will prepare kits containing the 5-day supply of study medications (investigational drugs/placebo) which will be sequentially numbered in accordance with the randomization tables. The contents of each kit (investigation drugs/placebo) will be indistinguishable. Study staff will establish symptom status at the baseline visit, and per pharmacy order, provide the participant the next numbered medication kit in the participant's stratum (no symptoms/mild symptoms). The study investigators, staff interacting with the participants are all masked to treatment assignment

A. Research Procedures

- 1. Study Procedures:
 - Day 0/1 Screening/Baseline Visit (in person)
 - Pre-screen via online screening form to confirm eligibility
 - Obtain informed consent for trial enrollment
 - Medical history
 - Medication history
 - Document symptoms (if any)

- o Take temperature, PO2, Pulse
- Q-T interval assessment

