During combination therapy for up to 48 weeks with peginterferon alfa-2a plus ribavirin, growth inhibition was observed in pediatric participants 5 to 17 years of age. Decreases in weight for age z-score and height for age z-score up to 48 weeks of therapy compared with baseline were observed. At 2years post-treatment, 16% of pediatric participants were more than 15 percentiles below their baseline weight curve and 11% were more than 15 percentiles below their baseline height curve. The available longer term data on participants who were followed up to 6 years post-treatment are too limited to determine the risk of reduced adult height in some patients [see Clinical Studies Experience

Drug interactions: Didanosine, zidovudine

Availability: FDA approved; commercially available Ribavirin will be supplied free of charge to all patients enrolled.

[figure not shown]
Generic name: Nitazoxanide Commercial name: ALINIA

For complete information please refer to the package inserts at http://dailymed.nlm.nih.gov/dailymed/nitazoxanide

Chemical name: 2-acetyloxy- N-(5-nitro-2-thiazolyl) benzamide

Source: Commercially available

 C_{12} H₉ N₃ O₅ S and the molecular weight is 307.3

Nitazoxanide is a light yellow crystalline powder. It is poorly soluble in ethanol and practically insoluble in water.

ALINIA Tablets contain 500 mg of nitazoxanide and the following inactive ingredients: maize starch, pregelatinized corn starch, hydroxypropyl methylcellulose, sucrose, sodium starch glycollate, talc, magnesium stearate, soy lecithin, polyvinyl alcohol, xanthan gum, titanium dioxide, D&C Yellow No. 10 Aluminum Lake, FD&C Yellow No. 6 Aluminum Lake, and FD&C Blue No. 2 Aluminum Lake.

ALINIA for Oral Suspension, when reconstituted with 48 mL of water, produces 60 mL of a homogeneous suspension with a pink color that contains 100 mg nitazoxanide per 5 mL and the following inactive ingredients: sodium benzoate, sucrose, xanthan gum, microcrystalline cellulose and carboxymethylcellulose sodium, anhydrous citric acid, sodium citrate dihydrate, maltodextrin, modified food starch, triacetin, FD&C Red No. 40 and artificial strawberry flavoring.

Pharmacokinetics

Absorption Single Dosing: Following oral administration of ALINIA Tablets or Oral Suspension, the parent drug, nitazoxanide, is not detected in plasma.

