Multiple dosing: Following oral administration of a single ALINIA Tablet every 12 hours for 7 consecutive days, there was no significant accumulation of nitazoxanide metabolites tizoxanide or tizoxanide glucuronide detected in plasma.

Bioavailability: ALINIA for Oral Suspension is not bioequivalent to ALINIA Tablets. The relative bioavailability of the suspension compared to the tablet was 70%. When ALINIA Tablets are administered with food, the AUC of tizoxanide and tizoxanide glucuronide in plasma is increased almost two-fold and the C_{max} is increased by almost 50%. When ALINIA for Oral Suspension was administered with food, the AUC of tizoxanide glucuronide increased by about 45-50% and the C_{max} increased by $\leq 10\%$.

Distribution: In plasma, more than 99% of tizoxanide is bound to proteins.

Elimination Metabolism: Following oral administration in humans, nitazoxanide is rapidly hydrolyzed to an active metabolite, tizoxanide (desacetyl-nitazoxanide). Tizoxanide then undergoes conjugation, primarily by glucuronidation.

Excretion: Tizoxanide is excreted in the urine, bile, and feces, and tizoxanide glucuronide is excreted in urine and bile. Approximately two-thirds of the oral dose of nitazoxanide is excreted in the feces and one-third in the urine.

Contraindications:

Hypersensitivity: ALINIA Tablets and ALINIA for Oral Suspension are contraindicated in patients with a prior hypersensitivity to nitazoxanide or any other ingredient in the formulations.

Drug interactions: Highly Protein Bound Drugs with Narrow Therapeutic Indices i.e. Tizoxanide, warfarin

Availability: FDA approved; commercially available Ribavirin will be supplied free of charge to all patients enrolled.

There is no current data that assess the risks of the use of all three drugs in combination.

A. Drug/Device Accountability and Storage Methods

Drug accountability logs and pharmacy records must be maintained at each pharmacy location and must be available for review upon request. Drug accountability logs and pharmacy records will be reviewed during monitoring visits and by the Research Pharmacist

B. Treatment Compliance

The study medication will be given in accordance with the protocol and the instructions of the treating investigator. The study drugs will be provided to participants to be self-administered. Participants will be asked to confirm medication dosing each day on daily logs and on the day 3 and day 6 call with research staff.

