The participant will then come to the study location at [name] to complete final screening for the trial eligibility. P02 will be measured and 6 lead portable electrocardiogram will be performed; if PO2<92% or QT interval is QTc interval > 450 mSEC the participant will be excluded. Females of childbearing potential will have a urine test to confirm that they are not pregnant.

Inclusion Criteria

- 1. Documented SARS-CoV-2 infection by qPCR assay without symptoms or with mild symptoms consistent with COVID-19 performed within the past 7 days
- 2. Age ≥21

Exclusion Criteria

- 1. COVID-19 symptoms requiring hospitalization
- 2. PO2 < 92%
- 3. Short of breath at time of enrollment
- 4. Retinal eye disease
- 5. Known glucose-6 phosphate dehydrogenase (G-6-PD) deficiency
- 6. Known chronic kidney disease, stage 5 or receiving dialysis
- 7. Current use of:
 - Class 3 AAD (amiodarone, dronaderone, dofetilide, sotalol)
 - Class 1A AAD (procainamide, quinidine, disopyramide)
 - Flecainide
 - SSRI: citalopram (Celexa), Escitalopram (Lexapro)
 - chlorpromazine
 - Cilostazol (Pletal)
 - Donepezil (Aricept)
 - Droperidol
 - Fluoconazole
 - Methadone
 - Ondansetron (Zofran)
 - Thioridazine
 - Macrolides (clarithromycin, erythromycin)
 - Fluroquinolones (ciprofloxacin, levofloxacin, moxifloxacin)
 - Tamoxifen citrate
- 8. Pregnancy or women who are breast feeding
- 9. Inability to tolerate oral medications
- 10. Allergy or prior adverse reaction to either hydroxychloroquine sulfate, ribavirin, or nitazoxanide
- 11. Allergy to adhesives
- 12. QTc interval > 450 mSEC for men and women
- 13. History of Torsade de Pointes VT or prior cardiac arrest or congenital long QT interval
- 14. Non-English-speaking

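### The allergy exclusions in sections 1.3 and 4.1 are narrower than the nitazoxanide contraindication in section 1.7: no eligibility rule covers a known allergy to a tablet ingredient

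*Combined protocol and SAP*

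**What the plan says.** Section 1.7 (Drugs/Devices/Biologics) gives a single contraindication for nitazoxanide. Its tablets and suspension are "contraindicated in patients with a prior hypersensitivity to nitazoxanide or any other ingredient in the formulations". The same section lists the inactive ingredients of the 500 mg tablet, among them "talc, magnesium stearate, soy lecithin, polyvinyl alcohol, xanthan gum, titanium dioxide" and three color additives.

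Two places turn drug allergy into an eligibility rule:

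- Section 4.1, exclusion 10: "Allergy or prior adverse reaction to either hydroxychloroquine sulfate, ribavirin, or nitazoxanide".
- Section 1.3: "People who are allergic or intolerant to NTZ, RBV or HCQ will be excluded".

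Both name the three active drugs and neither mentions ingredients. The two nearest other exclusions in section 4.1 are number 9, "Inability to tolerate oral medications", and number 11, "Allergy to adhesives".

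**The concern.** The rule that decides who is enrolled is narrower than the restriction that the protocol states for one of its own study drugs. A volunteer may know of an allergy to a listed ingredient such as soy lecithin from food or another medicine, without ever having taken nitazoxanide. That volunteer meets no exclusion criterion and could be allocated a tablet that section 1.7 says is contraindicated for them.

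What is at stake is the safety of an occasional individual and the internal consistency of the protocol. The trial's statistical properties are not in question.

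**Working it through.** No formula in the plan bears on this point, and there is no planned figure to reproduce. The check is a comparison of texts, followed by a rough size.

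**Step 1. Set the restriction beside the rules.**

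| Place | Reaction to the drug itself | Allergy to another tablet ingredient |
|---|---|---|
| 1.7, nitazoxanide contraindication | covered | covered |
| 1.3, design paragraph | covered (allergic or intolerant) | not mentioned |
| 4.1, exclusion 10 | covered (allergy or prior adverse reaction) | not mentioned |
| 4.1, exclusion 9 | general oral intolerance | not mentioned |
| 4.1, exclusion 11 | no | no (adhesives only) |

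The other 11 of the 14 exclusions do not concern allergy or tolerance. No criterion excludes people with a label contraindication in general, and none gives the investigator general discretion to exclude.

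**Step 2. Narrow the gap to what is left.** Someone who has already reacted to a nitazoxanide tablet, whatever component caused it, can be excluded under the prior-reaction wording of exclusion 10 or the intolerance wording of 1.3. What remains is an ingredient allergy known from another source in a person with no earlier reaction to the drug.

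**Step 3. Ask whether the exclusion list is meant to carry such restrictions.** Several cautions given for hydroxychloroquine in 1.7 reappear as explicit exclusions in 4.1: retinal disease, G-6-PD deficiency and tamoxifen. The list is therefore where the protocol puts drug-section restrictions into effect. The nitazoxanide restriction was carried over only in part.

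**Step 4. Check that the ingredient list fits the product.** The list in 1.7 belongs to a 500 mg tablet. The dosing line of the treatment plan in 1.3 counts 250 mg tablets, while a later line of the same plan gives 500 mg per tablet. The product dispensed is unresolved, so soy lecithin is an example conditional on the 500 mg product. For ribavirin, 1.7 lists the ingredients of a film-coated tablet, whereas the treatment plan dispenses capsules.

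**Step 5. Size.** Inputs: 35 participants per arm (section 1.5). The prevalence of a known allergy to a listed ingredient is an assumption of 0.5% to 2%; the documents give no figure.

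Expected number in the active arm = prevalence × 35:

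- 0.005 × 35 = 0.175
- 0.02 × 35 = 0.70

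That is about 0.2 to 0.7 people. The placebo arm is left out because the documents do not list the placebo ingredients.

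**The case against.** The strongest reply is that the gap would rarely survive contact with the site.

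- Section 4.4 has staff go over the eligibility and exclusion criteria with each interested volunteer.
- Section 1.3 requires medical and medication histories at the baseline visit, before randomization.
- Final screening is in person (section 4.1).
- Section 1.7 points to the label: "For complete information please refer to the package inserts at".
- A sensible reader could take nitazoxanide in exclusion 10 to mean the tablet as supplied.

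Most of this stands as mitigation. Each step is a chance to notice a declared allergy, but none tells staff to ask about ingredients or makes the answer a ground for exclusion. The label is cited for information and not as an eligibility rule.

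It is also fair to say that 1.7 is largely label text and that other restrictions in it, such as hemoglobinopathies under ribavirin, are absent from 4.1 too. That makes this one instance of a wider mismatch, but does not remove it.

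A reader might infer more than the documents support:

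- *That an ingredient allergy is the only history that could reveal the contraindication.* An earlier reaction to the tablet is already covered.
- *That such a volunteer will certainly pass screening.* This is only the literal reading of the criteria.
- *That all 70 participants are exposed.* Only 35 are planned for active nitazoxanide.
- *That the first dose is taken unsupervised at home.* Section 1.3 describes self-dosing when staff instruct it and a telephone call about two hours later, but does not state the place.
- *That a reaction would distort the toxicity comparison.* A reaction to a study tablet is properly an adverse event of the product given, and only grade 3 or higher events are recorded.

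**Conclusion.** The inconsistency is real and minor. The written eligibility rules do not cover part of the contraindication that the protocol states for nitazoxanide. The part left out is a known allergy to another tablet ingredient in someone with no earlier reaction to the drug.

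The expected number is about 0.2 to 0.7 of 35 in the active arm. This rests on an assumed prevalence of 0.5% to 2% that nothing in the documents anchors, and on the 1.7 ingredient list describing the product in the kits. It also takes no account of cases that staff review or history-taking would catch, so for a given prevalence it is an upper figure.

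Sample size, power, the endpoint and the primary analysis are unaffected. The documents do not support reading this as a threat to the trial's conclusions or as evidence that screening would fail in practice.

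**What to change.** 1. Reconcile the nitazoxanide contraindication in 1.7, the allergy sentence in 1.3 and exclusion 10 in 4.1 so that all three name the same set of allergies. Which set applies is for the sponsor and the clinical investigators to decide.
2. Carry the agreed wording into the online screening form, so that the question is put to every volunteer in the same way.
3. Confirm which nitazoxanide product is dispensed and reconcile the 250 mg and 500 mg statements in the treatment plan, so that any ingredient list used at screening matches the kits. Check the hydroxychloroquine, ribavirin and placebo products in the same step.

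The cost is a phrase in each affected section, one screening item and a product check with the research pharmacist. If the agreed wording turned out to exclude more people, the same assumed prevalence implies 0.005 × 70 = 0.35 to 0.02 × 70 = 1.4 volunteers lost per 70. No change to the analysis is needed.

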1.8 Specimen Collection

A. Primary Specimen Collection

The research specimens collected will be for:

- 1. Viral load
- 2. Antibody testing
- 3. Safety (CBC and chemistry)

Types of Specimens:

- Mid-turbinate self nasal swab will be collected at baseline and days 3, 6 and 10
- Blood specimen will be collected at baseline, day 14 and day 28
- Annotation: Specimens will be uniquely identified and marked with the participant's study ID and study time point. All primary collection devices (blood and nasal swab kits) will have a unique barcode that is linked to the participant study ID at the time of collection and sample registration.
- Transport: Nasal-swabs specimens (live virus is fully deactivated by the transport media) will placed in the packing materials supplied by the research laboratory (TGen) or designee shipped to Altasciences via Fed Ex promptly following specimen collection at the clinic and at home. The nasal swab specimens will be batched at Altasciences and shipped to TGen on a frequency to be determined by study enrollment. All shipping material, instructions and transport supplies will be provided to the participant within the collection kit. All blood specimens will be collected during clinic visits and transported for testing in accordance with institutional policy. Blood for clinical analyses (cbc, chem panel, magnesium will be directly transported to the RWJUH laboratory by the study staff. Blood drawn for antibody testing will be packaged and sent to RUCDR via UPS, using the materials and instructions provided by RUCDR. These samples will be processed, frozen, and stored at RUCDR until transport to the [name] Lab for analysis.
- **Processing**: All specimen processing will be in accordance with institutional policy.

- Storage: The blood specimens and the nasal swab specimens will be stored at their respective laboratories until the time of testing.
- Disposition: The antibody blood specimens and nasal swab specimens will be maintained until the end of study. Leftover specimens may be de-identified and may be used for other future research, e.g., validating viral load measurements with improved technologies or viral sequencing analysis.
- B. Secondary Specimen Collection N/A

1.9 Data Collection

A. Primary Data Collection

Data collection will occur at a baseline visit with follow-up data collected over the subsequent month as described below.

Location: Study site visits (baseline, day 14 & day 28) will take place at the designated RWJMS study location at [name] which is an Institutional Biosafety Committee (IBC) approved location to meet with SARS-Cov-2 positive individuals. Consent and all questionnaires will be completed electronically online. This questionnaire will include items on health and medical history, lifestyle, employment and patient contact, and demographics. At baseline, contact information (e-mail/phone) for the participant will be collected as well as contact information of 2 individuals who know the participant well who we can reach out to in case the participant falls ill.

Follow-up questionnaires will be administered daily for 10 days and on day 28 after entering the study. Follow-up questionnaires will include items on symptoms of COVID-19, reactions to the study medications and health status of household members since the last questionnaire Up to 3 daily automated reminders will be sent to remind participants to complete the surveys. In addition, participants will self-report their body temperature, PO2, and pulse daily through REDcap, daily for the first 10 days of the study period. Participants will receive automated email/text reminders to record this information daily. We will also call on days 3, 6 and 10 to confirm self specimen collection, check medical status and study drug dosing (on days 3 & 6) and questionnaire completion compliance. On day 14 participants will return for a blood draw and to return the ZIO AT monitoring device. On day 28, participants will return to the clinic for a final symptom assessment, a blood draw for immune function and CBC, pregnancy test, if applicable and final study drug accountability.

- Process of Data Collection: All in-person data collection will be overseen by the clinical study coordinator team conducting study visits, with questionnaires self-administered by participants. The blood specimens will be collected at the in-person visits (baseline, day 14 & 28). Participants will be responsible for reporting their own daily temperatures, PO2 and pulse.
- Timing and Frequency: Following the baseline visit and questionnaire, self-administered questionnaire data will be collected on for the first 10 days and on day 28 after entering the study. Data on temperature, PO2, pulse will be reported through REDCap daily for 10 days.
- Procedures for Audio/Visual Recording: N/A, no recordings planned
- Study Instruments: As described earlier, the questionnaires will collect demographic and health history and behaviors at baseline. They follow-up questionnaires will capture current signs and symptoms of potential infection and infection in household members.
- Ethnographic Studies, Interviews, Or Observation: N/A

 Participant Identifiers: Biospecimen and questionnaire data will be coded by study ID. A link between study ID and participant name/date of birth will be retained and available to approved study staff to link specimens to participants.

B. Secondary Data Collection

For participants who develop symptoms or seek clinical care for any medical, and grant permission to obtain records, we will access medical records related to their infection and subsequent care. We will review hospital records from acute illness resulting from COVID-19 including discharge summary, imaging, laboratory studies, and treatments. No medical records will be reviewed for participants who remain asymptomatic, and no data will be abstracted on unrelated conditions or previous health history.

- Type of Records: In those developing symptoms, medical records related to the possible infection will be abstracted. Relevant fields include diagnoses, lab values, imaging data, medications and other interventions, other inpatient care related to the infection, and disposition (e.g., discharge, death).
- Location: Study staff with authorized access to the RBHS and hospital electronic records will access those records directly. Records that are at outside locations or to which the researchers do not have authorized access will be requested directly from the facility. At the time of consent, each participant will be asked to sign a form authorizing the release of these data.
- Inclusion/Exclusion: Records will be abstracted from the date of randomization forward until the end of the 28-day active follow-up period. Charts will be reviewed by trained clinical study coordinators using secure connections.
- Data Abstraction Form(s): Each participant will be assigned a unique study identification number that will be linked to each completed electronic questionnaire as well as to the collected biospecimens. All questionnaires will be administered via and stored in REDCap software hosted by Rutgers Robert Wood Johnson Medical School ¹⁷.

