1.0 Research Design

1.1 Purpose/Specific Aims

The purpose of this study is to evaluate the efficacy of Nitazoxanide (NTZ), Ribavirin (RBV) and Hydroxychloroquine (HCQ) versus placebo in participants with proven SARS-CoV-2 infection who are asymptomatic or mildly symptomatic with COVID-19. Those with illness requiring hospitalization, or who present with hypoxia (PO2<92%) or shortness of breath at time of enrollment are excluded.

A. Objectives

In participants with proven SARS-CoV-2 infection who are asymptomatic or mildly symptomatic with COVID-19 randomly allocated to nitazoxanide, ribavirin plus hydroxychloroquine (NTZ, RBV + HCQ) or placebo.

Primary Objective:

To assess the rate of decline in viral load over the 10 days after randomization between participants treated with NTZ, RBV + HCQ for COVID-19 and placebo.

Secondary Objective:

- 1. To compare the proportion of participants with virus below LLOQ at day 10
- 2. To compare the proportion of participants who are asymptomatic and symptomatic at day 10
- 3. To compare the time of onset and frequency of the development of fever and other symptoms of COVID-19 in those who were asymptomatic at enrollment
- 4. To compare the progression in severity of COVID-19 symptoms (hospitalization and length of stay; admission to intensive care unit and number of days in unit; intubation, Death (any cause))
- 5. To compare the severity of disease in participants who develop symptoms of COVID-19
- 6. To compare the side effects of NTZ, RBV + HCQ compared to placebo
- 7. To determine whether baseline viral load predicts response to therapy
- 8. To assess the rate of decline in viral load over days 3 and 6 after randomization
- 9. To assess new, self-reported COVID-19 infection in household members

B. Hypotheses / Research Question(s)

We hypothesize that treatment with NTZ, RBV + HCQ decreases viral load and the progression of symptoms, or emergence of symptoms in those who are asymptomatic at baseline, in SARS-CoV-2-positive adults compared to placebo.

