- 4. Proportion of participants with progression of severity of COVID-19 symptoms (hospitalization and length of stay; admission to intensive care unit and number of days in unit; Intubation; Death (any cause))
- 5. Comparison of severity of disease in participants who develop symptoms of COVID-19 at all timepoints
- 6. Assessment of medication toxicity as measured by standard metrics
- 7. Q-T interval from baseline of > 60msec or QT > 500 msec)
- 8. Number of participants with undetectable viral load and absence of symptoms
- 9. Rate of decline in viral load at study days 3 and 6
- 10. New, self-reported COVID infection in household members

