Once participants are started on study drug, monitoring for prolongation of QTc or development of polymorphic ventricular tachycardia is required. The Zio AT (iRhythm Technologies, Inc.) is a mobile cardiac telemetry device that allows continuous monitoring of the QTc interval and heart rhythm abnormalities. The Zio AT consists of a small transdermal patch that is applied on the participant's upper chest and a gateway device (size of a cell phone) that has to be kept within 10 feet of the participant. The ECG signal is transmitted to iRhythm technologies via the internet using the gateway. The participant does not have to change batteries or do anything to the device for the 10-day monitoring interval. We have used this device clinically and participant compliance is excellent. The rhythm is monitored continuously for arrhythmias and our EP-cardiology team will be notified immediately for any run of ventricular tachycardia (VT) greater than 4 complexes and other significant arrhythmias (pauses greater than 3 seconds, heart block, atrial fibrillation). We are monitoring for any run of VT since we have found that most episodes of torsade de pointes VT are preceded by shorter runs of polymorphic VT. The participant can also

trigger a transmission by pressing a small button on the transdermal patch if they experience any cardiac symptoms. We will monitor the QTc with this device. We will obtain a baseline transmission at the initial visit after the participant has been deemed to be eligible based on the Kardia Mobile 6L QTc measurement. We will ask the participant to do a transmission for QTc measurement 2 hours after the first dose of study drug. These will be reviewed and QTc measured by our EP cardiology team. We will then monitor the QTc interval twice a day at two predetermined times. This type of monitoring is equivalent to what can be done in the hospital on telemetry and in practice may be superior since the protocol will be strictly adhered to and measurements made by an electrophysiologist. If QT interval increases from baseline of > 60msec or QT > 500 msec, the medications, if still being taken, will discontinued at that time. Participant QT will be monitored every 6 hours until the interval returns to baseline. If a serous arrhythmia is detected during the continuous monitoring, the study cardiologist and participant will be promptly contacted, and the participant will be directed to seek medical treatment as appropriate.

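### Section 1.9 B contradicts itself on record review for participants who stay asymptomatic, so the depth and verification of hospital outcomes can depend on a symptom status that treatment may change

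*Combined protocol and SAP*

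**What the plan says.** Section 1.9 B (Secondary Data Collection) sets the rule for medical records in three places:

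- The opening trigger: "For participants who develop symptoms or seek clinical care for any medical, and grant permission to obtain records, we will access medical records". A noun is missing after the word medical; the likely sense is any medical reason. The rest of the sentence confines access to records about the infection and the care that followed it.
- The exclusion, later in the same paragraph: "No medical records will be reviewed for participants who remain asymptomatic, and no data will be abstracted on unrelated conditions or previous health history".
- The scope, under Type of Records: "In those developing symptoms, medical records related to the possible infection will be abstracted".

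Abstraction runs from randomization to the end of the 28-day follow-up.

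Secondary endpoint 4 in Section 1.3 F is the proportion of participants whose COVID-19 progresses in severity. Its listed components are "hospitalization and length of stay; admission to intensive care unit and number of days in unit; Intubation; Death (any cause". Section 6.1 compares hospitalization, ICU admission, intubation and death between the arms by logistic regression, with groups analyzed as randomized.

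Section 1.1 B states the hypothesis: "We hypothesize that treatment with NTZ, RBV + HCQ decreases viral load and the progression of symptoms, or emergence of symptoms", the last part referring to participants who are asymptomatic at baseline.

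**The concern.** An outcome compared between randomized arms should be ascertained, and documented, in the same way in both. Here, access to the hospital chart turns partly on whether a participant develops symptoms after randomization. The trial hopes treatment will change exactly that. If it does, more active-arm participants end up in the group whose charts stay closed.

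The infection-only limit adds a second filter. Under Section 4.7 E, if the cardiac monitor detects a serious arrhythmia, "the participant will be directed to seek medical treatment as appropriate". If that participant has no COVID-19 symptoms and is admitted, the chart is outside abstraction because the participant stayed asymptomatic and because the condition is not the infection. Admissions for drug reactions would be expected mainly in the active arm.

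At stake are the completeness of length of stay and ICU days, the assignment of cause, and the evidence behind the causality assessment that Section 1.3 C asks of the investigator for each serious adverse event.

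**Working it through.** No figure in the plan is in dispute, so there is none to reproduce. The check compares the provisions and then adds an illustration on assumed figures.

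**1. Which provisions cover a symptom-free participant who is admitted?**

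| Provision | Covered? |
|---|---|
| 1.9 B, opening trigger | Yes as a person (sought care); the content is still limited to infection-related records |
| 1.9 B, exclusion | No |
| 1.9 B, Type of Records | No |
| 1.3 C, serious adverse events | Yes; in-patient admission and death qualify whatever the symptoms or cause |

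The first two rows cannot both be followed. The last row shows that the event itself has a separate route to detection.

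**2. Which parts of endpoint 4 have a source other than the chart?**

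- *Hospitalization and death:* yes. They are serious adverse events, collected from first dose through follow-up. Adverse events are reviewed in everyone on days 3, 6, 10 and 28 (schedule of events, Section 1.3 A).
- *ICU admission and intubation:* only as far as a serious adverse event report happens to describe them.
- *Length of stay, ICU days and verified cause:* none is described. The data list in Section 1.3 D names adverse events and care given to manage COVID-19, but no admission dates or ICU days. The questionnaires in Section 1.9 A cover COVID-19 symptoms, reactions to study medication and household health. Day 14 is scheduled for blood tests and device return, with no adverse event review between days 10 and 28.

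No section says which source determines the components of endpoint 4.

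**3. How large could the effect be?** The plan gives none of the rates needed, so all of these are assumptions:

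- p = true admission rate, equal in both arms (no treatment effect): 5%
- s = share who have symptoms at any time: 50% active, 80% placebo
- c = probability that an admission is captured in someone who never has symptoms
- admission is independent of symptoms, which is the worst case
- n = 35 per arm (Section 1.5)

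Captured rate = p × [s + (1 − s) × c].

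*Chart documentation.* On the narrow reading of Section 1.9 B, c = 0.

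- True admissions per arm: 35 × 0.05 = 1.75.
- Documented, active: 35 × 0.05 × 0.50 = 0.875. Documented, placebo: 35 × 0.05 × 0.80 = 1.40.
- Undocumented: 1.75 − 0.875 = 0.875 active and 1.75 − 1.40 = 0.35 placebo, a difference of 0.525, or about half an admission.

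*Occurrence of admission,* at different levels of capture through serious adverse event reporting:

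| c | Active | Placebo | Odds ratio (true value 1.00) |
|---|---|---|---|
| 0 | 2.5% | 4.0% | (0.025/0.975) ÷ (0.040/0.960) = 0.62 |
| 0.5 | 3.75% | 4.5% | 0.83 |
| 0.9 | 4.75% | 4.9% | 0.97 |
| 1 | 5.0% | 5.0% | 1.00 |

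With c = 0 and 80% symptomatic on placebo, the odds ratio runs from 0.87 (70% symptomatic on active) to 0.49 (40%). With c = 0.9 that range shrinks to 0.99 to 0.96. Changing p to 3% or 10% in the 50% versus 80% case gives 0.62 and 0.61 at c = 0.

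**The case against.** A reader might infer that hospital outcomes and drug-related admissions are themselves found or missed according to symptom status. The documents do not support this. Section 1.3 C makes every in-patient admission and every death a serious adverse event, and requires study-related toxicities and serious adverse events to be followed until resolution, with an exception for conditions unlikely to resolve. Adverse event review is scheduled for everyone. Section 1.9 A holds two outside contacts per participant in case of illness. The arrhythmia example makes the same point: Section 4.7 E has all participants monitored and the cardiology team notified at once, so the study would see the event. The odds ratio of 0.62 assumes that none of this works. It shows direction and is not an estimate.

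Three further arguments carry some weight:

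- Endpoint 4 is framed as progression of COVID-19 severity, so infection-related abstraction fits much of it. A COVID-19 admission would ordinarily involve symptoms, which opens the records. The fit fails for death, which counts from any cause, and Section 6.1 does not restrict hospitalization by cause.
- The exclusion does not touch participants with mild symptoms at entry, since they cannot remain asymptomatic.
- Section 4.7 E commits to collecting only the data the research needs, so wider record access has a privacy cost. That cost is small if access is tied to a reported admission, emergency visit or death.

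The opening trigger might be thought to settle the matter, because an admitted participant has sought care. It widens who is covered, but not what may be read, and the later sentence still contradicts it.

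**Conclusion.** The point holds as a matter of depth and verification. Section 1.9 B gives two incompatible rules for a participant without symptoms who seeks care. The records process is the only described source of length of stay, ICU days and confirmed cause, and it depends on a post-randomization status that treatment is hypothesized to change. Documentation of endpoint 4 and of drug-related admissions can therefore differ by arm.

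The size is unknown and probably small. The rule bites only on participants who never have symptoms, and few hospital events are likely among 35 per arm. The half-admission difference rests on an assumed 5% admission rate, assumed symptomatic shares of 50% and 80%, and admission independent of symptoms. The safety comparison as a whole is not shown to be biased: it rests on adverse event reporting, cardiac monitoring and blood tests, none of which depends on symptoms. With so few events, though, one admission of unverified cause or duration could matter to how the result is read. This is a cheap improvement, not a threat to the primary analysis of viral load.

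**What to change.** Reconcile the sentences in Section 1.9 B with one rule that does not depend on symptoms:

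- Request records for every reported hospitalization, emergency visit or death from randomization to day 28, whatever the symptom status or presumed cause.
- Abstract admission and discharge dates, ICU days, intubation, cause and outcome.
- Delete the bar on reviewing records of participants who remain asymptomatic, align the Type of Records item, and limit the exclusion of unrelated conditions to history before randomization.
- State in Section 1.3 F or 6.1 that these records, together with serious adverse event reports, are the source for endpoint 4 in both arms.

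The consent route largely exists: at consent, "each participant will be asked to sign a form authorizing the release of these data". The form's wording should be checked so that it covers admissions not related to the infection. The cost is a wording change to the protocol and possibly the release form, a few extra chart abstractions, and slightly wider access to participants' records.
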